RESEARCH PROTOCOL

Date	7/31/2023
Title	Evaluating the use of preventive cold saline to decrease bleeding associated with endobronchial biopsy
Principal Investigator	[name], BSN, RN
Sub-Investigators	[name], BSN, RN, CGRN
Research Specialist	[name], RN, CRN-BC
Department	Bethesda North Hospital, Endoscopy Department
Hatton #	23-037

Purpose of Study

Patients undergoing an endobronchial ultrasound and biopsy can experience bleeding during the biopsy. These biopsies are read in real time by pathologists who travel to the endoscopy unit during the procedure. Often, when this happens, the blood contaminates the pathology slides making the slide unreadable. This then requires more biopsies to be performed, thus prolonging the procedure, and increasing anesthesia time. One innovative way to reduce bleeding may be to irrigate the bronchial wall with cold saline, where the biopsy is to be taken, immediately before biopsy, thus causing vasoconstriction and possibly resulting in less blood contamination on the biopsy slides. The current study will evaluate this prophylactic irrigation with saline to control bleeding, thus resulting in a quicker diagnostic result of the biopsies.

Hypothesis or Research Question

- Hypothesis 1: Patients undergoing endobronchial ultrasound and biopsy who receive irrigation with cold saline prior to biopsy will experience a lower incidence of unreadable biopsy slides compared to patients undergoing endobronchial ultrasound and biopsy who do not receive irrigation with cold saline prior to biopsy.
- Hypothesis 2: Patients undergoing endobronchial ultrasound and biopsy who receive irrigation with cold saline prior to biopsy will experience a lower incidence of having to reperform biopsies in order to obtain readable slides compared to patients undergoing endobronchial ultrasound and biopsy who do not receive irrigation with cold saline prior to biopsy.
- Hypothesis 3: Patients undergoing endobronchial ultrasound and biopsy who receive irrigation with cold saline prior to biopsy will experience a lower incidence of stopping the procedure without biopsy results compared to patients undergoing endobronchial ultrasound and biopsy who do not receive irrigation with cold saline prior to biopsy.
- Hypothesis 4: Patients undergoing endobronchial ultrasound and biopsy who receive irrigation with cold saline prior to biopsy will experience a lower incidence of requiring epinephrine to control bleeding after the biopsy compared to patients undergoing

endobronchial ultrasound and biopsy who do not receive irrigation with cold saline prior to biopsy.

Background

Endobronchial ultrasounds are used to investigate lymph nodes and/or lesions within or next to the patient's lungs that are visible on ultrasound. The procedure can be used in the diagnosis or staging of cancer. Fine needle biopsies can be obtained through the endobronchial ultrasound scope, and the tissue obtained is immediately placed on cytology slides and promptly taken outside the room to the mobile cytology cart to be stained. The pathologist will then read the prepared slides in real time, offering feedback as to what cells are seen. However, red blood cells often contaminate the sample, due to bleeding from the biopsy site, and thus potentially cover up and block the obtained specimen. This causes more biopsies to be taken and prolongs the procedure and anesthesia time. During normal bronchoscopies, cold saline is used, and has been studied, to decrease bleeding in the airways. This study evaluates the use of cold saline irrigation BEFORE biopsies are taken to potentially decrease the risk of bleeding. Irrigating with cold saline preventatively BEFORE biopsies are taken is not common practice. Additionally,, there has been no research conducted investigating the use of cold saline prior to bronchial biopsies being taken to decrease bleeding. This study seeks to fill this gap in the literature.

Research Plan

- **Study Design**

This study will use a randomized, non-blinded, controlled design with two arms:

- Arm 1: Patient will receive irrigation with 120mL of cold saline 33-39 degrees Fahrenheit), delivered in two 60mL syringes, prior to biopsy
- Arm 2: Patient will receive standard care which involves biopsy without prior irrigation with cold saline.

- **Setting for the study**

The study will take place on Bethesda North Hospital's Endoscopy Department. This unit provides care to approximately 2-12 patients undergoing an endobronchial ultrasound and biopsy per week.

- **Participants**

The study will enroll 120 patients who meet the following inclusion/exclusion criteria:

Inclusion Criteria:

- Undergoing an endobronchial ultrasound and biopsy at Bethesda North Hospital

Exclusion Criteria:

- Under 18 years old
- Does not speak English
- Unable to consent to involvement in the research study

- Is pregnant
- Has a bleeding disorder/diagnosis
- Currently taking anticoagulant medications and not stopped for procedure
- Documented low platelets (<100,000)
- Had a biopsy taken immediately prior to the endobronchial ultrasound

Sample Size Determination: A power analysis was conducted using a small to medium effect size (0.3), power of 0.8, and level of significance 0.05. It was determined that 44 patients would be needed in each group, for a total sample size of 88 patients. To allow for the possibility of removing participants from the final analysis due to missing data, we plan to enroll 120 patients (60 in each group).

- **Data Collection**

Before the study begins, information about the study will be provided to the providers and endoscopy team members, including information about the study purpose, inclusion/exclusion criteria, and procedures.

When a patient who meets the inclusion/exclusion criteria arrives for an appointment, a nurse from the study team will describe the study, answer any questions the patient has, and if the patient wants to enroll in the study, the study team nurse will review the information consent form. After the patient provides written informed consent, the nurse will remove the next envelope out of a box of prefilled and sealed opaque envelopes. The envelope will provide the Subject ID number to be used on all study-related documentation and the study Arm that the patient has been randomized to, either:

1. Cold saline group
2. Standard care group

These envelopes will be filled using a computerized simple random number generator (1:1 randomization) prior to the start of the study.

In addition to the group assignment, the envelope will include a data collection form. Data will be recorded directly on this form during the patient's visit. The form will collect the following information:

- Whether patient was assigned to the cold saline group or the standard care group
- Patient demographics including age, gender, current anticoagulant medications, current cancer diagnoses
- Temperature of cold saline (cold saline group only)
- Time cold saline placed (cold saline group only)
- Volume of cold saline used for irrigation
- Time each biopsy was obtained
- Number of biopsies
- Gauge of needle used to perform biopsy
- Type of suction used (i.e. slow-pull or 5mL, 10mL)

- Number of slides prepared
- Number of slides that were successfully read
- Number of slides unable to be read due to blood on slide
- Whether another biopsy was attempted
- Whether the procedure was stopped without successful slide reading
- Whether patient needed epinephrine post-biopsy to stop bleeding
- Name of MD performing biopsy
- Start and end time of procedure

After the procedure, the RN will complete the data collection form and place the signed informed consent form and data collection form in the locked resource nurse's office in an area designated for study materials.

On the data collection forms, RNs are instructed to call a member of the study team immediately if there are any safety concerns related to the cold saline. If the study team receives a call about a safety concern, recruitment and enrollment of new participants will stop until the study team meets and reviews the incident with the pulmonologist involved and determines it is safe to continue. The study team includes nurses with clinical experience and expertise in endobronchial biopsy procedures. They will consult with the medical team if any adverse events arise. Any adverse events and serious adverse events will be reported to the IRB in compliance with IRB safety policies.

- **Intervention or experimental aspect of the study**

In patients randomized to Arm 1, the clinician will scan the cold saline using the infrared temperature scanner and confirm saline is between 33-39 degrees Fahrenheit. Then after identifying the lymph node or lesion to be biopsied on ultrasound, using the endobronchial ultrasound scope, two 60mL syringes of cold saline will be inserted, through the biopsy channel of the endobronchial ultrasound scope, directly onto the bronchial wall where the biopsies are to be performed. The saline will then be sucked out of the airway using the endobronchial ultrasound scope. The FNA needle or biopsy forceps will then be passed down the biopsy channel of the endobronchial ultrasound scope, and the biopsy will be obtained. Cold saline irrigation is part of the normal procedure and may cause coughing. The study may benefit these patients if the preventive cold saline irrigation prevents bleeding.

Patients randomized to Arm 2 will receive standard care that includes no irrigation with cold saline prior to the biopsy. After identifying the lymph node or lesion to be biopsied on ultrasound, the FNA needle or biopsy forceps will then be passed down the biopsy channel of the endobronchial ultrasound scope, and the biopsy will be obtained.

In both Arm 1 and Arm 2, TriHealth pulmonologists will conduct the endobronchial ultrasound and biopsy according to standard clinical practice. Patients will receive the same care procedure and biopsy that they would receive if they were not enrolled in the study. The only research procedure is that patients in Arm 1 will receive irrigation of the biopsy site with cold saline before the biopsy is performed. The rest of the procedure will follow standard clinical practice.

Data recorded on paper data collection forms will be entered into a password protected database. Only study team members will have access to the database. No personal information will be entered into the electronic database. Data will undergo range checks when entered in the database, and quality control procedures will be performed to ensure accuracy of the data in the electronic database.

- **Statistical Analysis**

Statistical analyses will be performed using Intellectus Statistics statistical software. The following analyses will be performed to address each hypothesis:

- Hypothesis 1: Patients undergoing endobronchial ultrasound and biopsy who receive irrigation with cold saline prior to biopsy will experience a lower incidence of unreadable biopsy slides compared to patients undergoing endobronchial ultrasound and biopsy who do not receive irrigation with cold saline prior to biopsy.

To compare the effects of the intervention, a Chi Square test will be used to compare frequency of unreadable biopsy slides among patients who received the cold saline irrigation compared to patients who did not receive the cold saline irrigation. A level of significance of $\alpha=0.05$ will be used.

- Hypothesis 2: Patients undergoing endobronchial ultrasound and biopsy who receive irrigation with cold saline prior to biopsy will experience a lower incidence of having to reperform biopsies in order to obtain readable slides compared to patients undergoing endobronchial ultrasound and biopsy who do not receive irrigation with cold saline prior to biopsy.

To compare the effects of the intervention, a Chi Square test will be used to compare frequency of having to reperform biopsies among patients who received the cold saline irrigation compared to patients who did not receive the cold saline irrigation. A level of significance of $\alpha=0.05$ will be used.

- Hypothesis 3: Patients undergoing endobronchial ultrasound and biopsy who receive irrigation with cold saline prior to biopsy will experience a lower incidence of stopping the procedure without biopsy results compared to patients undergoing endobronchial ultrasound and biopsy who do not receive irrigation with cold saline prior to biopsy.

To compare the effects of the intervention, a Chi Square test will be used to compare frequency of stopping the procedure without biopsy results among patients who received the cold saline irrigation compared to patients who did not receive the cold saline irrigation. A level of significance of $\alpha=0.05$ will be used.

- Hypothesis 4: Patients undergoing endobronchial ultrasound and biopsy who receive irrigation with cold saline prior to biopsy will experience a lower incidence of requiring epinephrine to control bleeding after the biopsy compared to patients undergoing endobronchial ultrasound and biopsy who do not receive irrigation with cold saline prior to biopsy.

To compare the effects of the intervention, a Chi Square test will be used to compare frequency of epinephrine administration to control bleeding after the biopsy among patients who received the cold saline irrigation compared to patients who did not receive the cold saline irrigation. A level of significance of $\alpha=0.05$ will be used.

Interim data analysis will occur (1) once approximately 1/3 of the participants have been enrolled in each group and (2) once approximately 2/3 of the participants have been enrolled in each group. If interim calculations at time (1) or time (2) note a significant difference in outcomes between groups, data collection will be completed at that time and final analysis will be completed.

Ethical Considerations

- **Informed consent**

All study staff will complete CITI training. A study staff member will meet with potentially eligible patients and describe the study and answer any questions. If the patient is interested and meets all the inclusion/exclusion criteria, the study staff will review the *Informed Consent Form* and obtain written informed consent. Patients will receive a copy of their signed Informed Consent form.

Informed Consent forms will be stored in a locked room that only staff will have access to. After the study closes, the signed Informed Consent forms will be boxed and sent to off-site storage and securely stored for 10 years after the close of the study. At that time, the hard copy forms will be shredded.

- **Privacy information**

Personal identifiers will not be entered into the electronic database. Hard copy data collection forms and Informed Consent forms will be stored in a locked room that only staff will have access to. Electronic data will be stored on a password-protected folder on the U drive. Only study staff will have access to the electronic study documents. After data analysis and dissemination is completed, hard copy forms will be boxed and sent to off-site storage and securely stored for 10 years after the close of the study. At that time, the hard copy forms will be shredded.

Cost/Budget

There will be no costs to conduct this study and no additional charges to patients.

Estimated Period of Time to Complete Study	
When will study begin?	5/26/2023
Protocol Development Completed	2 weeks
IRB Approval	6 weeks
Data collection	6 months
Data analysis	2 weeks
Presentation development (if applicable)	2 weeks
Manuscript Development (if applicable)	1 month
Journal submission process (if applicable)	4 months
Study closure	2 weeks

- **When and how will results be disseminated?**

Results will be disseminated internally to the TriHealth endoscopy team and system-wide through the TriHealth Research Council. Results will be disseminated nationally through presentation at a professional organization conference. Finally, results will be disseminated nationally and internationally by publication in a relevant peer-reviewed journal.

References

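### The pathologist is not masked to arm in a non-blinded trial, although slide readability is an undefined judgement and masked reading appears feasible at low cost

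*Combined protocol and SAP*

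**What the plan says.** The Study Design section declares the trial open: "This study will use a randomized, non-blinded, controlled design with two arms". No section keeps the pathologist, or any other assessor, unaware of the arm.

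On the reading itself, Purpose of Study says: "These biopsies are read in real time by pathologists who travel to the endoscopy unit during the procedure". Background says that tissue goes onto slides, which are "promptly taken outside the room to the mobile cytology cart to be stained", and continues: "The pathologist will then read the prepared slides in real time, offering feedback as to what cells are seen".

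The Data Collection section lists the item behind Hypothesis 1: "Number of slides unable to be read due to blood on slide". It gives no criterion or scale for an unreadable slide, and no second reader. The same form also records "Whether patient was assigned to the cold saline group or the standard care group". On who fills it in: "After the procedure, the RN will complete the data collection form".

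For Hypothesis 1, the Statistical Analysis section says that "a Chi Square test will be used to compare frequency of unreadable biopsy slides", at a significance level of 0.05.

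**The concern.** Two judgements are made on each slide: whether it can be read, and whether blood is the reason if it cannot. Without a written criterion there will be borderline cases. If the reader knows that saline was used and knows what the study hopes to show, those cases can drift toward the saline arm. That is detection bias. A larger sample does not remove it; it only makes the test more likely to declare it significant.

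The operator has to know whether the airway was irrigated. The pathologist does not. The one assessor whose judgement defines the Hypothesis 1 outcome is therefore the one who could most easily be masked, and the plan does not use that opportunity.

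The reading also feeds two later outcomes. Hypothesis 2 counts biopsies repeated to get readable slides, and Hypothesis 3 counts procedures ended without a result. A biased reading would carry into both through the live request for more tissue.

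**Working it through.** **The plan's own figure.** The Sample Size Determination paragraph gives effect size 0.3, power 0.8, alpha 0.05 and 88 patients. Reading 0.3 as Cohen's w for a two-sided 1-df chi-square test:

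N = (1.960 + 0.842)² / 0.3² = 87.2, rounded up to 88.

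Power is 0.804 at 88 and 0.908 at 120. The figure reproduces. It does not depend on blinding, so masking the reader leaves the sample size as it is.

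**Can reading be separated from treatment?** Set side by side, the text gives this sequence: irrigation and biopsy take place in the room; slides are carried out for staining; the pathologist then reads them and gives feedback. Nothing in that sequence requires the reader to know the arm. The protocol assigns the envelope to the study nurse and completion of the form to the RN. It does not say that the pathologist handles either.

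**Illustration of size.** From the plan: 60 patients per arm, chi-square test, alpha 0.05. Assumed, because the documents give no values:
- the true proportion of patients with an unreadable result, p, is the same in both arms (no saline effect), from 10% to 50%;
- a reader who knows the arm calls a share s of the truly unreadable saline-arm results readable, with s from 10% to 30%;
- there is one binary outcome per patient and a single two-sided test at full enrolment.

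The observed saline-arm rate becomes q = p(1 − s). With x unreadable results in the standard-care arm, y in the saline arm and p̄ = (x + y)/120, the Pearson statistic is

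X² = (x/60 − y/60)² / [p̄(1 − p̄)(2/60)].

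The rejection rate is the sum of Bin(x; 60, p) × Bin(y; 60, q) over all pairs with X² > 3.841. For example, p = 0.50 and s = 0.20 give q = 0.40, which is 30 against 24 expected unreadable results, and a rejection rate of 0.205.

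| True rate p | s = 0 | s = 10% | s = 20% | s = 30% |
|---|---|---|---|---|
| 10% | 0.050 | 0.054 | 0.067 | 0.089 |
| 20% | 0.050 | 0.058 | 0.085 | 0.135 |
| 30% | 0.052 | 0.068 | 0.119 | 0.210 |
| 40% | 0.051 | 0.074 | 0.149 | 0.286 |
| 50% | 0.055 | 0.091 | 0.205 | 0.392 |

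Where the inflation is material, nearly all rejections favour saline: 0.204 of the 0.205 at p = 50% and s = 20%.

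**The case against.** The strongest reply is that the plan openly declares a non-blinded design. This is an improvement that was passed over, not an error or a contradiction. The bias also needs a reader who both knows the arm and leans toward saline, and the documents state neither. The pre-study briefing names providers and the endoscopy team, not pathologists. All of that stands. The defensible statement is that masking is not specified, not that the pathologist is known to be unmasked.

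A reader might infer several stronger things that the documents do not support:

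- **That this is the primary outcome.** None is designated. Unreadable slides is the first of four hypotheses, each tested at 0.05.
- **That the pathologist reads outside the room.** The text says that slides are taken out to be stained and are then read. Reading at the cart is a strong inference, not a statement.
- **That masking costs nothing.** Feedback is live, so staff must withhold the arm in those exchanges. Some leakage is likely, and its frequency is unknown.
- **That three of the four outcomes rest on this reading alone.** Repeating a biopsy and stopping a procedure are also decisions of the operator, who knows whether saline was given. Epinephrine use does not depend on the slide reading.

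The illustration also has limits. At a low true rate with 10% leniency the inflation is negligible. The form collects slide counts, so a single binary outcome per patient is a simplification. The two planned interim looks are left out.

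**Conclusion.** The point holds in a limited form. The protocol neither masks the pathologist nor defines an unreadable slide, and its own description of the workflow suggests that masked reading could be done cheaply. This is an avoidable detection-bias risk on the Hypothesis 1 outcome and on the part of Hypotheses 2 and 3 that follows from the reading. It should be addressed, but it is not fatal to the trial.

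The size cannot be fixed from the documents. Over the assumed range, a nominal 5% rejection rate becomes 5-9% at a true unreadable rate of 10%, 6-14% at 20%, 7-21% at 30%, 7-29% at 40% and 9-39% at 50%. The upper figures need both a common outcome and substantial leniency, so they should not be quoted without the lower ones. If the pathologist in practice never learns the arm, this bias does not arise, and the remaining gap is that the protocol does not say so.

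**What to change.** - Change the design line to say that the operator and nurse are unblinded and the pathologist is blinded to arm.
- Label slides with the Subject ID only.
- Instruct room staff not to disclose the arm when slides are handed over or during real-time feedback.
- Have the pathologist record slides read, and slides unreadable because of blood, on a separate slip that carries the Subject ID and no arm. Attach it to the data collection form afterwards.
- Put a short written criterion for unreadable on that slip. This limits subjectivity even where masking fails.

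The cost is one protocol sentence, one slip, one staff instruction and some accidental unblinding during live feedback. No extra reader, procedure or patient is needed, and the planned 120 is unchanged.

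The protocol should also state the limit of the change: it does not mask the operator's decisions to repeat a biopsy or stop the procedure, or the use of epinephrine (Hypothesis 4). If masking the reader proves impracticable, the protocol should say why and keep the written criterion.

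### The arm is revealed at consent, before the biopsy target is seen, and no rule keeps randomised patients in their assigned arm, so arm-aware removal or reclassification is possible though not shown

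*Combined protocol and SAP*

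**What the plan says.** **Timing of allocation.** Under Data Collection, a patient who already meets the criteria arrives, is told about the study and consents. Then: "After the patient provides written informed consent, the nurse will remove the next envelope out of a box of prefilled and sealed opaque envelopes". Each envelope holds the Subject ID, the arm and the data collection form used during the visit. The text says the envelope is removed, not opened. Opening at that point is implied, because its contents are needed from then on.

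**Eligibility.** The single inclusion criterion presupposes a biopsy: "Undergoing an endobronchial ultrasound and biopsy at Bethesda North Hospital". The last exclusion criterion is "Had a biopsy taken immediately prior to the endobronchial ultrasound". No re-check is described between consent and the procedure.

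**Order of steps in the room.** In the intervention section, Arm 1 begins with a scan of the saline temperature. It continues: "Then after identifying the lymph node or lesion to be biopsied on ultrasound", after which the saline is instilled. In Arm 2 the target is likewise identified during the procedure, before the needle or forceps is passed.

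**Blinding and analysis.** Study Design describes the trial as non-blinded. Sample Size Determination says that "44 patients would be needed in each group, for a total sample size of 88 patients", and raises enrolment to 120 so that participants with missing data can be removed. Each of the four tests under Statistical Analysis contrasts patients who had the irrigation with patients who did not. No as-randomised or intention-to-treat population is stated.

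**The concern.** Randomisation makes the arms comparable at the moment of allocation. Here some events that decide whether a patient yields usable data can come after that moment, and the people present know the arm. The plan does not say what happens to a randomised patient who turns out to have no target, is found to meet the prior-biopsy exclusion, or is assigned saline but not irrigated.

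Two features of the text leave the outcome open. A patient who is never biopsied has no slide data and so falls naturally among those removed for missing data; nothing says who decides on removal or whether that person is blind to arm. And under the wording by irrigation received, a patient assigned saline but not irrigated belongs either nowhere or with the controls. Either route can make the compared groups differ for reasons other than the saline.

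A secondary issue is that target, needle gauge and suction type can all be chosen with the arm known. Gauge and suction are recorded, but nothing requires the choice to be made before the arm is seen.

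**Working it through.** **1. The plan's own figure.** Inputs from Sample Size Determination: effect size 0.3, power 0.8, significance level 0.05. Reading 0.3 as Cohen's w for a two-sided 1-df chi-square test:

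N = (1.960 + 0.842)² / 0.3² = 87.2, rounded up to 88, or 44 per arm. Noncentral chi-square power at N = 88 is 80.4%. The stated figure reproduces. The margin is 120 − 88 = 32 patients, or 32/120 = 26.7%.

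**2. Cost of keeping everyone as randomised.** Assume a share u of randomised patients contributes no treatment effect, so w becomes 0.3 × (1 − u). The documents give no u; 5% to 15% is an assumption. The noncentrality is 120w².

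| u | w | 120w² | Power |
|---|---|---|---|
| 0 | 0.300 | 10.80 | 90.8% |
| 5% | 0.285 | 9.75 | 87.7% |
| 10% | 0.270 | 8.75 | 84.1% |
| 15% | 0.255 | 7.80 | 79.8% |

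These figures assume no other losses from the 120. A second model counts unbiopsied patients as non-events in both arms, with assumed control rates of 30% to 60% among those biopsied. At 60 per arm it gives 91.8% with none unbiopsied, 86.0% to 87.9% at 10%, and 78.5% to 82.9% at 20%. The two models agree that dilution is affordable.

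For comparison, removing 10% evenly from both arms leaves N = 108 and power 87.7%. Even removal is therefore not the hazard; uneven removal is.

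**3. What uneven removal could do.** All rates here are assumed.

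*Moderate example.* No true effect, failure rate 50%. Ten percent of the saline arm is removed, and those patients had 80% failure. The remaining saline rate is (0.50 − 0.10 × 0.80) / 0.90 = 46.7%, a spurious gap of 3.3 points. For scale, w = 0.3 at an average rate of 50% is a difference of 2 × 0.3 × √(0.5 × 0.5) = 30 points. An exact calculation with 54 against 60 patients, without continuity correction, gives a type I error of 6.5%, against 5.5% with nobody removed.

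*Worst case.* No true effect, 60 per arm, and k patients with the event removed from the saline arm only. Exact two-sided type I error:

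| Event rate | k = 0 | k = 2 | k = 4 | k = 8 |
|---|---|---|---|---|
| 20% | 5.0% | 8.0% | 15.8% | 48.8% |
| 30% | 5.3% | 6.5% | 10.9% | 28.8% |
| 40% | 5.1% | 6.0% | 8.6% | 19.6% |
| 50% | 5.5% | 5.9% | 7.3% | 14.0% |

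This bounds what deliberate, one-sided removal could do. It is not a forecast. A larger enrolment margin replaces lost numbers but does not undo selection of this kind.

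**The case against.** **Eligibility is presumed settled on arrival.** This stands. A reader might infer that ineligible or unbiopsied patients will be randomised. The documents do not say so. Enrolment starts from a patient who already meets the criteria, and a prior biopsy that is planned, or done before arrival, could be known in time. Only one taken in the same session could not. Late ineligibility is an inference from the order of events.

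**Nobody is authorised to drop patients by arm.** This also stands. The only removal described is for missing data. A reader might infer that staff will drop patients knowing the arm; the text leaves that possible and goes no further. Nor is this a failure of concealment before consent, since the envelopes are sealed and opaque.

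**The arms do not first differ after the target is seen.** This is correct. In Arm 1 the saline temperature scan comes before target identification, so delaying the envelope requires that sequence to be reconciled.

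**The size is small and assumed.** This is partly right. Power stays above 80% at 5% and 10% dilution and misses by 0.2 points at 15%. The moderate selection example adds about one point of type I error. It also cannot apply to unbiopsied patients, who have no slides to fail. The larger figures need extreme one-sided removal.

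**One sentence on the analysis population would suffice.** It would cure the greater part. It would not stop target, needle and suction from being chosen with the arm known.

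**Conclusion.** The concern holds as a gap that leaves bias possible. Allocation is revealed at consent, the target is identified later, the team is not blinded, removal from the analysis is foreseen without a rule on who decides, and the tests are worded by irrigation received. Together these allow a randomised patient to be dropped with the arm known or moved to the other group.

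The documents do not show that this will happen or how often. Retaining an assumed 5% to 15% of such patients as diluted cases at N = 120 leaves power between 87.7% and 79.8%, so there is little statistical reason not to keep them. The distortion from selective removal ranges from slight (6.5% type I error in the moderate example) to serious in the worst case, entirely according to the assumed rates. The sample size itself is not in dispute. The change is worth making because it is cheap.

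**What to change.** 1. **Analysis.** Replace the wording by irrigation received with a comparison by assigned arm, including all randomised patients. State in advance the grounds for any removal, and have it decided by someone blind to arm.
2. **Timing.** Keep consent at arrival. Open the envelope in the procedure room once the target is identified and the prior-biopsy exclusion is checked. Do the saline temperature check beforehand for every consented patient, so that it no longer reveals the arm, and reconcile the Arm 1 sequence in the intervention section with this.
3. **Pre-allocation record.** Before opening, write the intended target, needle gauge and suction type on a sheet kept outside the sealed envelope, because the present form is inside it.

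**Cost.** Protocol wording; a separate sheet; chilled saline prepared for every consented patient and partly discarded; a brief pause during the procedure, which matters in a study motivated by procedure and anaesthesia time; and someone already in the room to open the envelope. The required number stays at 88, within the planned 120.

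**Limit.** Once the envelope is open, knowledge of the arm can still influence choices on later passes.
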